10.5.8.2.2. Recording Adverse Events

The AE reporting period for safety surveillance begins when the subject is initially included in the study (date of first signature of informed consent) and continues up to 30 days after the last study drug administration. If an AE is not resolved or stabilized by this time, the Sponsor in consultation with the Investigator will decide whether to continue to monitor the AE or closeout the event in the database if no further follow-up is necessary.

Any SAE suspected to be related to the study drug must be reported whenever it occurs, irrespective of the time elapsed since the last administration.

Investigator and study personnel will record all AEs and SAEs whether received through an unsolicited report by a subject, elicited during subject questioning, discovered during physical examination, laboratory testing, and/or other means by recording them on the eCRF and SAE Report Form, as appropriate. The following information should be recorded on the AE eCRF:

- Description including onset and resolution dates
- Whether it met SAE criteria
- Severity
- Relationship to study drug or other causality
- Action taken with study drug

- Outcome

For SAEs, events occurring secondary to the primary event should be described on the SAE Report Form in the narrative description field.

The following should be considered when recording SAEs:

- Death is an outcome of an event. The event that resulted in the death should be recorded and reported on the SAE Report Form and eCRF.
- For hospitalizations, surgical, or diagnostic procedures, the illness leading to the surgical or diagnostic procedure should be recorded as the SAE, not the procedure itself. The procedure should be captured in the narrative as part of the action taken in response to the illness.

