11.2. Determination of Sample Size

Subjects will be randomized as follows:

- Cohort 1: 36 subjects in 2:1 randomization ratio (24 subjects to etrasimod 2 mg and 12 subjects to placebo)
- Cohort 2: 42 subjects with SALT I < 95 at Baseline in 4:1:2 randomization ratio (24 subjects to etrasimod 3 mg, 6 subjects to etrasimod 2 mg, and 12 subjects to placebo)

Assuming a 15% drop-out rate from the study over 24 weeks, at least 35 treatment completers (20 subjects to etrasimod 3 mg, 5 subjects to etrasimod 2 mg, and 10 subjects to placebo from Cohort 2; plus subjects from Cohort 1 with SALT I < 95 at Baseline) at Week 24 will provide at least 80% and 47% power to detect a treatment difference of 20% for etrasimod 3 mg and etrasimod 2 mg from placebo, respectively, in the percent change from Baseline in SALT I at Week 24 by a 2-sample t-test using a 2-sided significance test level of 0.05 and common standard deviation (SD) of 17.8%.

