11.9.3. Extent of Exposure

The duration of time on study and time on study drug will be summarized for each treatment using descriptive statistics. The number of subjects on study drug for certain time intervals will also be summarized. The total subject-years on study drug and total subject-years on study will also be included in this summary.

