3.4 Schedule of Events

For the statistical analysis, DB Treatment Period will include 24 weeks treatment; OLE Period will include 28 weeks treatment and 4 weeks SFU. The date at which the subject is randomized will be referred to as the “Day 1/Baseline”. Subjects will be requested to attend the following scheduled visits for the DB Treatment Period from their Day 1/Baseline visit: Weeks 1, 2, 4, 8, 12, 16, 20, 24 visits as applicable (Week 1 visit is applicable to Cohort 2 only). For the OLE Period, subjects will attend scheduled visits at Week 24 (this will be same as Week 24 in the DB Treatment Period), and Weeks 25, 28, 36, 44, and 52. Subjects who terminate the study drug early in the DB Treatment Period or OLE Period should have SFU Visits 2 weeks and 4 weeks after the last dose of study drug. Visits subjects make to the clinic outside the visit window are recorded as unscheduled visits. Refer to Schedules of Assessments (Appendix 1 and Appendix 2 in the protocol) for more details.

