11.1 Adverse Events

AEs will be coded according to the MedDRA, Version 24.1, and will be summarized overall and by treatment group for across both study periods and for each study period separately.

Treatment emergent adverse events (TEAEs) are defined as any AEs with onset date during or after the first study treatment dose. See Appendix 2 for handling of completely or partially missing dates for AEs. AEs starting on the first study treatment dosing date and related to a pre-dose study assessment will not be considered as TEAE. In the case where it is not possible to define an AE as treatment emergent or not, the AE will be classified as treatment emergent.

Furthermore, TEAEs will be assigned to the DB Treatment Period or OLE Period depending on their onset date – if the AE onset date is before the date of first dose in OLE, the AE will be assigned to the DB Treatment Period AE. If the AE had an onset on or after the date of first dose in OLE, the AE will be assigned to an OLE Period. AEs starting on the Week 24 and related to a pre-dose study assessment will be assigned to DB Treatment Period.

An overall summary table of adverse events will be provided. The number of events and the frequency count and percentage of subjects who experienced an AE, TEAE, TEAE by maximum reported relationship, TEAE by maximum reported Common Terminology Criteria for Adverse Events (CTCAE) severity, serious AE (SAE), serious TEAE, TEAE leading to study drug

discontinuation, TEAE leading to study discontinuation, treatment emergent AE of Special Interest (AESI) and AE leading to death will be presented.

Of note, prior to each database lock (primary and final), AESIs will be flagged as such by the Sponsor Clinical Development/Medical teams from the subset of AEs that will have been classified programmatically as Targeted Medical Events (TMEs) based on an exhaustive list of SOCs and PTs provided by the Sponsor. The list of AEs deemed as AESIs will be finalized prior to each database lock.

Unless otherwise specified, a subject experiencing a TEAE multiple times within the same PT will be counted only once for the corresponding PT. Similarly, if a subject experiencing multiple TEAEs within the same SOC, the subject will be counted only once for that SOC. TEAEs will be sorted by decreasing order of total frequency of SOC and PT within each SOC.

Frequency and percentage of subjects who experience TEAE will be summarized by PT and also by SOC and PT.

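### The AE tables have no exposure-time denominator although the double-blind and open-label windows differ in length, and the SAP omits the protocol's subject-years without declaring it

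*SAP*

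**What the plan says.** **AE tables.** SAP 11.1 assigns a TEAE to the double-blind (DB) period if it starts before the first open-label extension (OLE) dose, and to the OLE otherwise. It sets no end date for a TEAE. The main tables are counts and percentages of subjects: "Frequency and percentage of subjects who experience TEAE will be summarized by PT and also by SOC and PT". The tables by relationship, severity, seriousness and AESI follow the same pattern. The overall table adds the number of events, and full-study tables are also listed. No AE table divides by time.

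**Windows.** SAP 3.4 sets 24 weeks of treatment for the DB period and adds that "OLE Period will include 28 weeks treatment and 4 weeks SFU". Protocol 10.5.8.2.2 says that AE collection "continues up to 30 days after the last study drug administration". SAP 11.2 uses the same unequal split for low lymphocyte counts: the DB window closes before the Week 24 dose, and the OLE window runs to the second follow-up visit.

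**Exposure.** Protocol 11.9.3 plans time on study, time on drug and numbers of subjects on drug by time interval, and then states: "The total subject-years on study drug and total subject-years on study will also be included in this summary". SAP Section 9 gives exposure in days, dose interruptions and compliance. It contains no subject-years and no time on study. SAP Table 4 lists four changes from the protocol (OLE baseline, FAS, Per Protocol Set, OLE FAS), and this is not one of them.

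**OLE columns.** SAP Appendix 1 shows OLE data under 2 mg, 2 mg-3 mg and 3 mg. The 2 mg column combines Cohort 1 subjects who finished or left the OLE before Amendments 2.0/2.1 took effect with subjects of either cohort who stopped before moving to 3 mg.

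**The concern.** Long-term safety is a secondary objective, and the OLE has no concurrent placebo. A reader will naturally set the OLE percentages against the DB percentages, or one OLE column against another. A crude percentage depends on how long subjects were watched as well as on risk. With unequal windows, a difference in percentages can appear with no change in risk, or a real change can be hidden. The subject-years that would let a reader see this were promised in the protocol and are absent from the SAP.

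**Working it through.** **1. The plan's own figure.** The documents state no AE rate. Their only derived design figure is the power in Protocol 11.2: "at least 80% and 47% power to detect a treatment difference of 20% for etrasimod 3 mg and etrasimod 2 mg from placebo", with completers given as "20 subjects to etrasimod 3 mg, 5 subjects to etrasimod 2 mg, and 10 subjects to placebo from Cohort 2", "by a 2-sample t-test using a 2-sided significance test level of 0.05 and common standard deviation (SD) of 17.8" percent. The noncentrality is 20 / (17.8 × √(1/n1 + 1/n2)).
- 20 v 10: 2.90 on 28 df, power 79.97%.
- 5 v 10: 2.05 on 13 df, power 47.6%.

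Both agree with the plan to rounding. They do not bear on this point, and the AE incidences used below are assumptions.

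**2. Window lengths for a subject who completes both periods.**
- DB: 24 × 7 = 168 days.
- OLE on treatment: 28 × 7 = 196 days. With the 30-day tail: 226 days.
- Ratios: 226/168 = 1.345 and 196/168 = 1.167. Using the 4-week follow-up instead of 30 days gives 224/168 = 1.333.

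**3. Effect on a crude percentage with the same constant hazard and full follow-up.** OLE percentage = 1 − (1 − p)^ratio.

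| DB incidence p | OLE, 226 days | OLE, 196 days |
|---|---|---|
| 5% | 6.7% (+1.7 points) | 5.8% (+0.8) |
| 10% | 13.2% (+3.2) | 11.6% (+1.6) |
| 30% | 38.1% (+8.1) | 34.0% (+4.0) |
| 50% | 60.6% (+10.6) | 55.5% (+5.5) |

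The 226-day column applies the on-drug hazard to the 30 days off drug, so it is the upper of the two. A rate removes the artefact. For p = 10%, the DB rate is −ln(0.90)/(168/365.25) = 22.9 per 100 subject-years. The OLE rate is −ln(1 − 0.1321)/(226/365.25) = 22.9.

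**4. When the direction changes.**
- Break-even: the OLE percentage is not higher if the mean OLE hazard is at or below 168/226 = 0.743 of the DB hazard.
- Falling hazard, for a subject on etrasimod throughout (assumed Weibull, shape k): OLE/DB cumulative hazard = (394/168)^k − 1. For k = 0.5, 0.8 and 0.9 this is 0.531, 0.978 and 1.154, so a DB 30% becomes 17%, 29% and 34%.

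**5. Dropout.** Protocol 11.2 gives "Assuming a 15% drop-out rate from the study over 24 weeks". Assume that those subjects leave at mid-period with a 30-day tail: mean DB window = 0.85 × 168 + 0.15 × (84 + 30) = 159.9 days. With 0%, 15% or 30% OLE dropout at mid-period (assumed), the mean OLE window is 226, 211.3 or 196.6 days. The ratios are 1.41, 1.32 and 1.23.

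**6. Between OLE columns.** A subject who stops after one week contributes 7 + 30 = 37 days, or 37/168 = 0.22 of a DB window. That subject sits in the OLE 2 mg column, while a subject who completes the OLE contributes about 226 days.

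**The case against.** A reader might infer that OLE percentages are higher by construction. The documents do not support that. It needs a similar, roughly constant hazard and near-complete OLE follow-up. Protocol 1.2 describes one front-loaded effect (heart-rate reduction, largest on the first day), and OLE entrants are selected by reaching Week 24 and passing the Protocol 4.3 criteria. Short exposure in the OLE 2 mg column pushes the other way. What stands is that the extra window can only add to an OLE completer's own percentage, while the net comparison can go either way.

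Nor are AEs reported only as crude percentages per period: the overall table has event counts, and full-study tables exist. Neither supplies what is missing. The counts have no time denominator. The full-study tables keep a Placebo column that includes etrasimod time for placebo subjects who enter the OLE.

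The other side has four further arguments:
- Protocol 11.9.2 itself plans AEs as proportions of subjects, and nothing promises rates per subject-year. Restoring subject-years would leave every AE table unchanged. This is correct: the subject-years are a protocol commitment, and the adjusted rates are an improvement.
- Subject-years on drug can be approximated as n × mean days / 365.25 from the planned exposure tables. This is true for drug time. Time on study and time to first event cannot be recovered that way.
- The documents plan no DB-versus-OLE test, and the OLE differs in dose, control and selection. Rates would not remove that confounding.
- The shift is modest against noise. For an arm of 24 at 30%, one standard error is √(0.3 × 0.7/24) = 9.4 points, and 8.1 points is about two subjects.

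The last two arguments limit how much weight an OLE comparison can bear, adjusted or not.

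**Conclusion.** The point holds as a matter of comparability, at modest weight. Crude DB and OLE percentages rest on nominal windows that differ by a factor of 1.35 (1.17 on treatment), and the OLE columns differ by more among themselves. The illustrated shift of about 3 to 11 points for DB incidences of 10% to 50% assumes an equal constant hazard, full follow-up and the 30-day tail. Its size and sign depend on the hazard shape and on dropout, which crude percentages cannot show.

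The randomised DB comparison is largely unaffected. All arms share the 24-week window, and the 30-day tail for subjects who do not enter the OLE follows the same rule in every arm.

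The omission of subject-years is a separate finding that needs no assumption: Protocol 11.9.3 promises them, SAP Section 9 does not provide them, and Table 4 is silent. It is not the cause of the unequal windows.

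**What to change.** 1. In SAP Section 9, restore total subject-years on drug and on study by treatment group and period. If the omission is intended, declare it in Table 4 with a reason.
2. In SAP 11.1, beside the crude percentages in the DB and OLE tables, add exposure-adjusted incidence: subjects with an event per 100 subject-years at risk, with time censored at the first event. Do this for any TEAE, serious TEAE, TEAE leading to study drug discontinuation, and AESI.
3. Optionally, show events starting after the last dose in a separate row for each period.

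The cost is SAP wording and a few columns built from dates already collected. Exposure-adjusted incidence assumes a roughly constant rate, so the crude percentages should stay. It also does not correct for the OLE 2 mg column being partly defined by early stopping; a footnote should say so.

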11.2 Clinical Laboratory

For quantitative laboratory test, descriptive statistics will be presented for data related to chemistry, hematology (including coagulation) and quantitative urinalysis. Observed values and change from baseline values will be presented for each post-baseline visit. Frequencies and percentages of subjects in each result category will be provided for qualitative urinalysis data.

Shift tables from baseline to each post-baseline visits describing shifts to abnormality (low or high) will be provided as well. Only subjects with a baseline result and a result at the specified visit for the parameter will be considered.

Separate listings of all data for chemistry, hematology (including coagulation), urinalysis and pregnancy test will be provided.

In addition, separate listings of data for chemistry, hematology (including coagulation), and urinalysis will be provided for each parameter where a subject had at least one abnormal result.

Incidence of hepatic enzyme elevations will be summarized by visit. The following hepatic enzyme elevations will be reported:

- ALT > 1, >2, > 3, > 5, > 8, > 10, and > 20 x upper limit of normal (ULN)
- AST > 1, > 2, > 3, > 5, > 8, > 10, and > 20 x ULN
- ALT or AST > 3, > 5, > 10, and > 20 x ULN
- ALP > 1, > 1.5, > 2, > 3, > 5, > 8, > 10, and > 20 x ULN
- GGT > 1, > 2, > 3, > 5, > 8, > 10, and > 20 x ULN
- Total bilirubin >1, > 1.5, >2, and >3 x ULN
- ALT or AST > 3 x ULN AND total bilirubin > 1.5 x ULN
- ALT or AST > 3 x ULN AND total bilirubin > 2 x ULN
- ALT or AST > 3 x ULN AND ALP > 1.5 x ULN
- Symptomatic elevation in ALT or AST, defined as an ALT or AST elevation > 3 x ULN in temporal association with nausea, vomiting, anorexia, abdominal pain, or fatigue, where temporal association is defined as onset of symptoms within +/- 14 days of the elevation.

Incidence of absolute lymphocyte count decrease at any time during a study period (post-dose on Day 1 to pre-dose on Week 24 for the DB Treatment Period and post-dose on Week 24 to the 2nd SFU visit for the OLE Period) will be summarized. The following categories will be presented:

- Grade 1, defined as an absolute lymphocyte count ≥ 0.8 to $< 1.02 \times 10^9/L$
- Grade 2, defined as an absolute lymphocyte count ≥ 0.5 to $< 0.8 \times 10^9/L$
- Grade 3, defined as an absolute lymphocyte count ≥ 0.2 to $< 0.5 \times 10^9/L$

- Grade 4, defined as an absolute lymphocyte count ≥ 0.0 to $< 0.2 \times 10^9/L$
- Any Grade 3 or 4
- Any Grade 1 to 4

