10.5.7.2. Total WBC, WBC Differential, Lymphocyte Counts, and Infections

Etrasimod prevents lymphocyte egress from lymphoid tissues, resulting in a reduction in peripheral lymphocyte count and lymphocyte availability for recruitment to sites of inflammation. To minimize the risk of unintentional unblinding of treatment assignment, site staff including Investigators will be blinded to total white blood cell (WBC) count, WBC differential (percentage and absolute number), and lymphocyte subset results during the Double-Blind Treatment Period. Investigators should minimize review of WBC count and differential, and lymphocyte subset results obtained by other health care providers caring for study subjects when review of those data is not required to ensure the safety of study subjects.

In the Double-Blind Treatment Period, total WBC count, WBC differential, and lymphocyte subset results will be monitored by an IMM. The IMM will not be involved in any other aspects of study conduct or data analysis. If these laboratory values require follow-up during the Double-Blind Treatment Period, the IMM will notify the Investigator and provide instruction. Blinded values may be released to treating physicians and Investigators as deemed medically necessary.

The Investigator will not be blinded to laboratory results during the Open-Label Extension. Investigators should refer to [Appendix 5](#) for laboratory adverse events aside from ALC decreases.

ALC reduction is an on-target effect of etrasimod treatment. However, if ALC is confirmed below the 0.2×10^9 cells/L limit, study drug should be interrupted and should not be re-initiated if the ALC remains below this threshold. Investigators will repeat complete blood count with differentials weekly until $ALC > 0.5 \times 10^9$ cells/L. Re-initiation of the study drug should only be considered when $ALC > 0.5 \times 10^9$ cells/L. If a subject in the Open-Label Extension has a treatment interruption due to $ALC < 0.2 \times 10^9$ cells/L, then that subject may be re-initiated at 2 mg etrasimod and maintained for the rest of the Open-Label Extension without escalation to 3 mg etrasimod (Section [6.3.2](#)).

Refer to Section [10.5.7.3](#) for information on monitoring for signs and symptoms of infections and diagnostic work-up and treatment of infections.

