2.2.1.4 Safety Endpoints

- Incidence and severity of adverse events (AEs) throughout the DB Treatment Period
- Incidence and severity of laboratory abnormalities and change from Baseline in laboratory values (to include hematology, serum chemistry, coagulation, and urinalysis) at Weeks 1 (Cohort 2 only), 2, 4, 8, 12, 16, 20, and 24
- Incidence of clinically significant vital sign abnormalities and changes from Baseline at 1-, 2-, 3-, and 4-hour post-dose on Day 1 as well as Weeks 1 (Cohort 2 only), 2, 4, 8, 12, 16, 20, and 24
- Electrocardiograms (ECG) at 4-hour post-dose on Day 1 as well as Weeks 12 and 24
- Holter Monitoring on Day 1 (Cohort 2 only) and Week 1 (Cohort 2 only)*
- Physical examination findings (abnormalities will be recorded and summarized as medical history or AEs, as applicable)

* The statistical analysis to be performed for these endpoints will be described in a separated SAP (refer to Section 1)

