4.4 Descriptive Statistics

All continuous variables will be summarized by presenting the number of subjects, mean, SD, median, minimum, and maximum. Categorical variables will be summarized using frequencies and percentages. Summary tables will be presented by treatment and visit, when applicable.

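### Neutrophil and total white-cell decreases are not tabulated by grade or worst value, although the laboratory safety endpoint is incidence and severity

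*SAP*

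**What the plan says.** SAP 2.2.1.4 gives the double-blind endpoint as "Incidence and severity of laboratory abnormalities and change from Baseline in laboratory values" and names hematology among the panels covered. SAP 2.2.2.2 repeats this for the open-label extension, and Protocol 11.9.1 has the same endpoint.

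SAP 11.2 defines severity categories for two groups:

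- Liver tests, in multiples of the upper limit of normal: "Incidence of hepatic enzyme elevations will be summarized by visit".
- ALC, in Grades 1 to 4: "Incidence of absolute lymphocyte count decrease at any time during a study period".

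All other quantitative tests, neutrophils and total WBC included, receive:

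- Descriptive statistics by visit. SAP 4.4 fixes their content: "All continuous variables will be summarized by presenting the number of subjects, mean, SD, median, minimum, and maximum".
- Low/high shifts by visit: "Shift tables from baseline to each post-baseline visits describing shifts to abnormality (low or high) will be provided as well".
- A listing of all values, and a further listing that "will be provided for each parameter where a subject had at least one abnormal result".

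SAP 4.3 admits a retest, unscheduled or early-termination value to a visit only when no scheduled value is available.

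Protocol 6.6 and 10.5.7.2 blind site staff to WBC, its differential and lymphocyte subsets during the double-blind period. An Independent Medical Monitor (IMM) reviews these results and contacts the Investigator if follow-up is needed, and values can be released on medical grounds. The blinding ends with the double-blind period.

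**The concern.** An endpoint that includes severity needs an output that shows severity by arm. A neutrophil count just under the laboratory's lower limit and one far below it are both simply low in the shift table. A subject who is low at baseline and falls further stays in the low-to-low cell.

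The study drug lowers circulating lymphocytes, and the protocol names infection as a risk (Protocol 1.2 and 10.5.7.3). It also treats low WBC and neutrophil counts as reasons not to enrol (exclusion criterion 23). How often each arm had a marked fall in these counts is therefore a question the study report should answer. The double-blind period matters most, because it holds the randomized placebo comparison. It is also the period in which sites are least likely to record such a fall as an adverse event.

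**Working it through.** No calculation settles this point. The check sets the endpoint against the analysis text and the output list.

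**Step 1. What each parameter receives (SAP 11.2 and Appendix 3; double-blind / extension table numbers).**

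| Output | Liver tests | ALC | Neutrophils, total WBC |
|---|---|---|---|
| Descriptive statistics by visit | 14.3.4.1.1 / .2 | 14.3.4.2.1 / .2 | 14.3.4.2.1 / .2 |
| Low/high shift by visit | 14.3.4.5.1 / .2 | 14.3.4.6.1 / .2 | 14.3.4.6.1 / .2 |
| Severity categories | 14.3.4.12.1 / .2 (by visit) | 14.3.4.13.1 / .2 (any time) | none |
| Listing of abnormal results | 14.3.4.9 | 14.3.4.10 | 14.3.4.10 |

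Tables with severity categories: 2 hepatic + 2 lymphocyte = 4. Those covering neutrophils or total WBC: 0 in either period. SAP Table 4, which records departures from the protocol, does not mention narrowing the endpoint.

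**Step 2. Whether the visit tables can stand in.** The shift table has no cell finer than low. The visit minimum shows the depth of one value per arm and visit, but not how many subjects came near it. Neither table follows a subject across visits. SAP 2.2.1.4 schedules 8 post-baseline double-blind laboratory visits in Cohort 2 (Weeks 1, 2, 4, 8, 12, 16, 20, 24) and 7 in Cohort 1. One low subject at each of 8 visits is compatible with a single subject or with eight different ones.

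**Step 3. Retests.** Protocol Appendix 5 asks for repeat testing of clinically significant Grade 3 and 4 laboratory abnormalities. If the scheduled value exists and the repeat is lower, SAP 4.3 keeps the repeat out of that visit's shift and minimum. It then appears only in a listing.

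**Step 4. Whether AE tables can stand in.** TEAEs are tabulated by maximum CTCAE grade (SAP 11.1; Table 14.3.1.5.1 for the double-blind period), so a low count recorded as an AE is graded there. To get there in the double-blind period:

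- Protocol 10.5.4 makes the Investigator record clinically relevant laboratory changes, but sends the differential and ALC to the process in 10.5.7.2.
- Under 10.5.7.2 the Investigator learns of the count if the IMM makes contact or the value is released.
- The only numeric on-treatment limits in that section are for ALC.
- Protocol Appendix 4 grades only laboratory abnormalities considered clinically significant.

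A low neutrophil count can therefore pass through the double-blind period without becoming a graded AE. In the extension this obstacle is absent, but the missing table is still missing.

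**The case against.** The strongest reply is that nothing is lost. Every hematology value is in Listing 16.2.8.2, abnormal results are listed again in Table 14.3.4.10, and the deepest summarised value per arm and visit appears as the minimum. SAP Appendix 1 orders listings by treatment group, so with about 78 planned subjects a reader could count by hand. SAP 11.2 also supplies the elements that Protocol 11.9.4 asks for (descriptive statistics, listings, shifts and changes from baseline) and adds the hepatic and lymphocyte categories. The stated mechanism concerns lymphocytes, which are the cells the SAP grades.

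Much of this stands, and it rules out three stronger readings:

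- A reader might infer that the severity of neutropenia or leukopenia is never reported. The listings, visit minima and AE tables show otherwise.
- A reader might infer that these counts are hidden from Investigators throughout. The blinding covers the double-blind period only, with IMM contact and medical release as exceptions.
- A reader might extend the point to platelets, hemoglobin, creatinine, creatine kinase and every other ungraded analyte. Investigators see those results throughout and can record and grade them as AEs. No passage requires every analyte to be graded.

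What the reply does not answer is that a listing is not an incidence by arm. SAP 11.2 does not say that the listings will carry a grade, so a reader would have to grade and count each subject by hand. Protocol 11.9.4 sets out general laboratory summaries. It does not remove severity from the endpoint in 11.9.1.

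**Conclusion.** The point holds for neutrophils and total WBC, in both periods. The endpoint includes severity, and no planned table gives either parameter by grade or by worst value. It matters more in the double-blind period, where the AE route is weak rather than closed.

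This is a gap in reporting. No data are missing and the efficacy analyses are untouched. Its size in subjects cannot be given, because the documents contain no rates of low neutrophil or WBC counts and no correlation between visits. The conclusion rests on the text of SAP 11.2 and the table titles in Appendix 3. The separate table layouts, which were not available, could contain more than the titles show.

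**What to change.** In SAP 11.2 and Appendix 3, add for neutrophils and total WBC, by arm and by period:

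- The number and percentage of subjects by worst post-baseline CTCAE grade at any time, in the form and over the period limits already used for ALC. State that scheduled, retest, unscheduled and early-termination values all count.
- A shift from baseline grade to worst post-baseline grade.

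State the CTCAE version. Protocol Appendix 4 and SAP 11.1 cite CTCAE without one, and the examples in Protocol Table 11 cover only ALT, AST and lung function, so the grade limits for these two parameters must be taken from the version named.

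The cost is SAP wording and about four programmed tables (2 forms × 2 periods), all from data already collected.
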